8.3. Discontinuation

8.3.1. Withdrawal of Patients

A patient has the right to withdraw from the study at any time. If a patient discontinues from the study, an Early Termination (ET) visit (as shown in the Schedule of Assessments, Section 7.3) will be performed, and the Sponsor and site monitor should be notified as soon as possible. In addition, a Follow-up Phone Call will be performed 8 weeks (\pm 5 days) following the patient's last dose of study drug to collect concomitant medications, procedures, and adverse events. Patients who withdraw from the study will not be replaced.

Patients should be permanently discontinued from ALXN1210 treatment if any of the following occur during the study:

- Serious infusion reaction (such as bronchospasm with wheezing or requiring ventilator support or symptomatic hypotension, refer to Appendix B) or serum sickness-like reactions manifesting 1 to 14 days after drug administration;
- Severe uncontrolled infection;
- Pregnancy or planned pregnancy; or
- If the Alexion Medical Monitor or the Investigator deems it to be in the best interest of the patient.

The Investigator should speak with the Medical Monitor prior to discontinuing a patient's study treatment. If a patient is discontinued from study drug, the patient should be encouraged to return for the remainder of his or her scheduled protocol visits until starting a different complement-targeted therapy.

The reason for the treatment or study discontinuation will be recorded on the eCRF.

If a patient is discontinued from the study with an ongoing AE or an unresolved laboratory result that, in the opinion of the Investigator, is significantly outside of the reference range and clinically significant (Section 11.4), the Investigator will attempt to provide follow-up until a satisfactory clinical resolution of the laboratory result or AE is achieved.

If a female patient is permanently discontinued from ALXN1210 treatment due to pregnancy, the Investigator will attempt to follow-up until the outcome of the pregnancy (see Section 11.8).

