14.5. Patient Disposition

All patients will be included in the summaries of patient disposition, which will describe the frequency and percentage of patients screened and treated and who completed or withdrew from the study, along with reason for withdrawal from the study.

The numbers of patients who are treated, discontinue treatment (along with reason for treatment discontinuation), complete or withdraw from the Primary Evaluation Period (along with reason for withdrawal), enter the Extension Period, and complete or withdraw from the Extension Period (along with reason for withdrawal) will be tabulated.

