7.1. Study Patients

7.1.1. Disposition of Patients

A summary of patient disposition for all patients will be presented and will include a summary of the number and percentage of screened patients, screen failures, and treated patients. The number and percentage of patients who completed the study through the end of the Primary Evaluation period or discontinued/withdrew from the study through the end of the Primary Evaluation period, along with reason for discontinuation/withdrawal will be presented.

The number and percentage of patients in each analysis set will be tabulated.

By-patient data listings with disposition will be provided as well as a listing of patients who did not meet the inclusion/met the exclusion criteria.

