7.2.2. Secondary Analyses

Descriptive statistics for the secondary endpoints will be produced for each visit where applicable, by naïve, previously eculizumab-treated patients and total.

- Percentage change in LDH from baseline to Day 183 (Week 26)
 - Absolute LDH levels, and the change and percent change from baseline, will be summarized at all study visits up to Day 183 (Week 26) by both observed case (OC) and LOCF. Baseline is defined as the average of all assessments analyzed by the central laboratory prior to first study drug administration.
 - The number (%) of patients achieving LDH levels at or below 1.0 times upper limit of normal ($1.0 \times \text{ULN}$) and levels at or below $1.5 \times \text{ULN}$ will be displayed.
 - Mean ($\pm 95\%$ CI) of absolute LDH levels, and the change and percent change from baseline will be plotted over time, by naïve and previously eculizumab-treated patients.
- Transfusion avoidance (TA)
 - Point estimates and 2-sided 95% exact CIs will be computed. Patients who withdraw from the study due to lack of efficacy during the Primary Evaluation Period will be considered as non-responders and will be counted in the group

- needing transfusion. For patients who withdraw from the study for any other reason during the Primary Evaluation Period, their data up to the time of withdrawal will be used to assess TA.
- A summary of the number of pRBC transfusion requirements up to Day 183 study will be presented including number of transfusion episodes and units transfused.
 - Change in quality of life (QoL), as measured by Pediatric FACIT-Fatigue questionnaire from baseline to Day 183 (Week 26)
 - The scoring guideline for the Pediatric FACIT-Fatigue instrument will be used to calculate a FACIT-Fatigue score. Please refer to Section 9.4 for a more detailed description of the Pediatric FACIT-Fatigue score and the scoring methods.
 - Absolute scores, change from baseline, and percent change from baseline in FACIT-Fatigue scores will be summarized by both OC and LOCF at baseline and at the study visits where this assessment is collected up to Day 183 (Week 26).
 - At each study visit, the proportion of patients who showed an improvement of at least 3 points for the Pediatric FACIT-Fatigue scores will be summarized by point estimates and 2-sided 95% exact CIs.
 - Proportion of patients with stabilized hemoglobin

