 - Point estimates and 2-sided 95% exact CIs will be computed. Patients who withdraw from the study due to lack of efficacy during the Primary Evaluation Period will be considered as non-responders and will be counted in the group who did not meet the stabilized hemoglobin definition. For patients who withdraw from the study for any other reason during the Primary Evaluation Period, their data up to the time of withdrawal will be used to assess stabilized hemoglobin.
 - Percentage change in free hemoglobin from baseline to Day 183 (Week 26)
 - Absolute free hemoglobin values, and the change and percent change from Baseline, will be summarized by both OC and LOCF at all study visits up to Day 183 (Week 26). Baseline is defined as the last non-missing assessment value prior to the first study drug infusion.
 - Mean (\pm 95% CI) of free hemoglobin, and the change and percent change from baseline will be plotted over time, by naïve and previously eculizumab-treated patients.
 - Proportion of patients with breakthrough hemolysis
 - Point estimates and 2-sided 95% exact CIs will be computed. Patients who withdraw from the study due to lack of efficacy during the Primary Evaluation Period will be considered as non-responders and will be counted in the group with breakthrough hemolysis. For patients who withdraw from the study for any other reason during the Primary Evaluation Period, their data up to the time of withdrawal will be used to assess breakthrough hemolysis.
 - The number of any treatment emergent MAVEs (n) and number of patients with events (n, %) will be displayed. Each of the MAVE categories will be similarly

summarized. Patients having multiple MAVEs within a category will be counted once in that category.

By-patient data listings containing all secondary endpoints will be produced.

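### The SAP counts lack of efficacy as non-response only when the patient leaves the study, so a child who stops ALXN1210 for lack of efficacy can still be scored as a success

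*SAP*

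**What the plan says.** SAP 7.2.2 applies the same pair of rules to transfusion avoidance, stabilized hemoglobin and breakthrough hemolysis. The first is "Patients who withdraw from the study due to lack of efficacy during the Primary Evaluation Period will be considered as non-responders". The second covers the remaining exits: "For patients who withdraw from the study for any other reason during the Primary Evaluation Period, their data up to the time of withdrawal" are what the endpoint is judged on. SAP 4.2 explains that the first rule was added to match studies ALXN1210-PNH-301 and -302.

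The protocol keeps stopping drug apart from leaving the study. Section 8.3.1 lists grounds for permanently stopping ALXN1210. Lack of efficacy is not among them by name; the only ground that could take it in is the general one, "If the Alexion Medical Monitor or the Investigator deems it to be in the best interest of the patient". A child who is off drug is encouraged to "return for the remainder of his or her scheduled protocol visits until starting a different complement-targeted therapy". The same section has the reason for either kind of discontinuation entered on the eCRF.

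Protocol 14.5 tabulates patients who "discontinue treatment (along with reason for treatment discontinuation") separately from those who complete or withdraw from the Primary Evaluation Period. SAP 7.3.2.1 makes the same distinction for adverse events. SAP 7.1.1 does not: it tabulates patients who completed and those who "discontinued/withdrew from the study through the end of the Primary Evaluation period, along with reason for discontinuation/withdrawal will be presented". SAP 4.1 nevertheless declares no change from the protocol's analyses.

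**The concern.** The non-responder rule is there so that an efficacy failure counts as a failure even if the child has not yet had a transfusion, a qualifying hemoglobin fall or a breakthrough event. It looks only at why a child left the study. Where the decision about efficacy is attached to stopping the drug, the rule has nothing to act on.

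No SAP text fills the gap. SAP 7.2.1.1 refers missing data back to each analysis. Protocol 9.7 prohibits other complement inhibitors, but the SAP gives starting one no consequence for these endpoints. The resulting error would favour the drug. In a report on about 12 children, shown by naïve and previously treated group as well as in total, one child moves the estimate noticeably.

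**Working it through.** **Step 1: the possible courses.** Take a child who stops ALXN1210 before Day 183 because it is not working, and apply the SAP text literally.

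| Course | Text that applies | Score |
|---|---|---|
| Leaves the study, reason coded lack of efficacy | Non-responder rule | Failure on all three endpoints |
| Leaves the study, another reason coded, no event so far | Any-other-reason rule, data to exit | Success |
| Stays in the study off drug, no event to Day 183 | Neither rule | Success by default |
| Had the endpoint event before stopping | Endpoint definition | Failure on that endpoint, possibly success on the others |

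Only the second and third courses are misclassified. In the third, the SAP also does not say whether data collected after stopping drug count towards Day 183.

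**Step 2: the most exposed endpoint.** Naïve children enter with LDH at least 1.5 × ULN (Protocol 8.1, criterion 4a). For them, breakthrough hemolysis requires LDH at least 2 × ULN after an earlier fall below 1.5 × ULN on therapy (SAP 5.1.2). A naïve child whose LDH never falls below 1.5 × ULN cannot meet that definition, whatever the symptoms. Only the non-responder rule could count that child as a failure.

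**Step 3: size.** The plan states no figure on this point to reproduce. Its one planning figure is about 13 enrolled for at least 10 evaluable completers (Protocol 14.2). That leaves room for 3 of 13, or 1 − 10/13 = 23.1%, not to complete, but no dropout rate is given from which 13 could be derived.

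The SAP specifies two-sided 95% exact intervals. For x successes in n, the Clopper-Pearson limits are the 0.025 quantile of Beta(x, n − x + 1) and the 0.975 quantile of Beta(x + 1, n − x). When x = n, the lower limit is 0.025^(1/n) and the upper is 1. For n = 12 (the report this SAP covers, SAP 4):

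- 12/12: lower limit 0.025^(1/12) = 0.735, giving 100% (73.5 to 100).
- 11/12: upper limit 0.975^(1/12) = 0.998 and lower limit 0.615, giving 91.7% (61.5 to 99.8).

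For breakthrough hemolysis, reported as the proportion with the event, the same child moves 0/12 = 0% (0 to 26.5) to 1/12 = 8.3% (0.2 to 38.5).

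The documents do not give the split into naïve and previously treated children, so the group sizes below 10 are assumed. Every row assumes one such child and no other failures.

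| n | Scored as success | Scored as failure | Fall in estimate (points) | Fall in lower limit (points) |
|---|---|---|---|---|
| 13 | 100% (75.3 to 100) | 92.3% (64.0 to 99.8) | 7.7 | 11.3 |
| 12 | 100% (73.5 to 100) | 91.7% (61.5 to 99.8) | 8.3 | 12.0 |
| 10 | 100% (69.2 to 100) | 90.0% (55.5 to 99.7) | 10.0 | 13.7 |
| 8 (assumed) | 100% (63.1 to 100) | 87.5% (47.3 to 99.7) | 12.5 | 15.8 |
| 5 (assumed) | 100% (47.8 to 100) | 80.0% (28.4 to 99.5) | 20.0 | 19.4 |
| 4 (assumed) | 100% (39.8 to 100) | 75.0% (19.4 to 99.4) | 25.0 | 20.4 |

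**The case against.** A reader might infer that the protocol sends every failing child first to drug discontinuation, so that the rule is routinely bypassed on all three endpoints. The documents do not support this. Protocol 8.3.1 sets out no lack-of-efficacy pathway. Because planned visits run only until another complement-targeted therapy starts, a switch may well bring study exit, which is the event the rule tests. If the site codes that exit as lack of efficacy, the rule fires. The eCRF reason list is not in the documents, so nobody can say from them which reason would be entered at either event.

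Nor does a child who stays in the study off drug fall under the any-other-reason clause, which covers only those who leave. For that child, events off drug may still count through Day 183, which would not flatter the drug. A child judged to be failing may also have been transfused or had a breakthrough event already.

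It would likewise go too far to call the case invisible. The SAP provides by-patient listings of disposition, exposure, compliance and all secondary endpoints, and with 12 patients a missed infusion would stand out. One can also argue that the Protocol 14.5 count still applies, since SAP 4.1 declares no change. However, the SAP 7.1.1 text omits it. Protocol 11.7 does not regard lack of drug effect as an adverse event, so the table of adverse events leading to discontinuation need not show the case either.

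Finally, the rule was chosen to match the adult studies, and Protocol 7.2 relies on extrapolation from adults. That is a good reason to keep the rule available, but not to leave the off-drug child undefined.

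These points narrow the concern without closing it. Listings let a careful reader find the child, but the reported proportion and interval would not change.

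**Conclusion.** The gap is real but narrow. It needs a child who stops ALXN1210 for lack of efficacy before Day 183, is event-free on the endpoint in question, and either remains in the study off drug to Day 183 or leaves with a different recorded reason. Such a child can be scored as a success. Breakthrough hemolysis in naïve children is the most exposed.

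Each such child shifts the overall proportion by 7.7 to 10 points at 13 to 10 patients, and by 12.5 to 25 points in assumed groups of 8 to 4. These figures illustrate scale and do not predict that the case will occur. No figure in the documents is wrong. The endpoints are secondary and descriptive, with no hypothesis test, so the type I error rate is not at issue and the primary PK/PD endpoint is untouched. The change is worth making because it is cheap and removes a possible bias in the drug's favour.

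**What to change.** - **SAP 7.2.2, all three endpoints.** Extend the non-responder trigger to any patient who, before Day 183, stops study drug or leaves the study for lack of efficacy, or starts another complement inhibitor because of inadequate response.
- **Data after stopping drug.** State whether observations made off drug, and after a switch, count towards each endpoint. List every patient who stops drug or switches before Day 183, with the recorded reason, because a vague code such as investigator decision could defeat the extended trigger too.
- **Consistency with the adult studies.** Keep the present study-withdrawal-only definition as a supporting analysis, so that results remain comparable with ALXN1210-PNH-301 and -302.
- **SAP 7.1.1.** Restore the Protocol 14.5 count of treatment discontinuations with reason, separate from study withdrawals, since SAP 4.1 declares no change from the protocol.

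The cost is SAP wording, one disposition row and one supporting table. The reason for treatment or study discontinuation is already collected on the eCRF (Protocol 8.3.1), as are concomitant medications (Protocol 9.7). The downside is a possibly slightly less favourable proportion. Only scoring and reporting change, and no rule for managing patients is affected.

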5.1.2. Secondary Endpoints

The secondary endpoints include:

- Percentage change in LDH from baseline to Day 183 (Week 26)
- Transfusion avoidance (TA), defined as the proportion of patients who remain transfusion-free and do not require a transfusion through Day 183 (Week 26)
- Change in quality of life (QoL), as measured by Pediatric Functional Assessment of Chronic Therapy (FACIT) Fatigue questionnaire (patients ≥ 5 years of age), from baseline to Day 183 (Week 26)
- Proportion of patients with stabilized hemoglobin, defined as avoidance of a ≥ 2 g/dL decrease in hemoglobin level from baseline in the absence of transfusion through Day 183 (Week 26)
- Percentage change in free hemoglobin from baseline to Day 183 (Week 26)
- Proportion of patients with breakthrough hemolysis, defined as at least one new or worsening symptom or sign of intravascular hemolysis (fatigue, hemoglobinuria, abdominal pain, shortness of breath [dyspnea], anemia, major adverse vascular event [MAVE, including thrombosis], dysphagia, or erectile dysfunction) in the presence of elevated LDH as follows:
 - For patients who enter the study naïve to complement inhibitor treatment, elevated LDH $\geq 2 \times$ ULN after prior LDH reduction to $< 1.5 \times$ ULN on therapy
 - For patients who enter the study stabilized on eculizumab treatment, elevated LDH $\geq 2 \times$ ULN.

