6.3. Full Analysis (FAS)

The Full analysis set (FAS) will consist of all patients in the Safety Set with a baseline and 1 secondary endpoint measurement post-first ALXN1210 dose.

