7. STATISTICAL ANALYSIS

All data collected in this study will be documented using summary tables, figures, and data listings. For categorical variables, frequencies and percentages will be presented by naïve, previously eculizumab-treated patients and total; for continuous variables, descriptive statistics (n, mean, median, standard deviation [SD], minimum, maximum) will be presented by naïve, previously eculizumab-treated patients and total.

Descriptive statistics for PK parameters will include the number of observations, mean, SD, coefficient of variance (CV), median, minimum, maximum, geometric mean, and geometric %CV.

Clinical central laboratory samples that meet the definition of TTH will be identified and all potassium, ALT, AST, magnesium, phosphorous, and LDH samples affected by TTH will be excluded from analysis of all efficacy and safety endpoints, with the exception that the LDH values will be used for the qualification of breakthrough hemolysis. The TTH samples from the central lab will be defined as having serum potassium ≥ 6 mmol/L and LDH $\geq 2 \times$ ULN.

A small portion of the data may not go through source data verification (SDV) process due to the COVID-19 pandemic. The non-SDV'd data will be flagged in listings.

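### Patients who leave event-free for reasons other than lack of efficacy count in effect as successes on three secondary endpoints, and no worst-case bound is planned beside the proportions

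*SAP*

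**What the plan says.** SAP 7.2.2 uses one two-part rule for transfusion avoidance (TA), stabilized hemoglobin and breakthrough hemolysis. A patient who leaves the study for lack of efficacy during the Primary Evaluation Period counts as a failure. For a patient who leaves for any other reason, "their data up to the time of withdrawal will be used to assess TA"; likewise "their data up to the time of withdrawal will be used to assess stabilized hemoglobin" and "their data up to the time of withdrawal will be used to assess breakthrough hemolysis". Each result is a point estimate with a two-sided exact 95% interval.

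SAP 5.1.2 defines TA as the "proportion of patients who remain transfusion-free and do not require a transfusion through Day 183 (Week 26"). Stabilized hemoglobin has the same Day 183 horizon. The breakthrough definition states none.

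The Full Analysis Set in SAP 6.3 is "all patients in the Safety Set with a baseline and 1 secondary endpoint measurement post-first ALXN1210 dose", so 26 weeks of follow-up are not required. SAP 7 states that "frequencies and percentages will be presented by naïve, previously eculizumab-treated patients and total".

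On missing data, SAP 7.2.1.1 defers to the individual analyses. SAP 7.2.1.5 names last observation carried forward (LOCF) as the sensitivity analysis where applicable, and SAP 7.2.2 assigns it only to LDH, FACIT-Fatigue and free hemoglobin. Protocol 14.11.1 covers only a missing Day 1 value and quality-of-life instruments.

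**The concern.** TA and stabilized hemoglobin are statements about the whole period to Day 183. A patient who leaves in week 6 without a transfusion has shown six transfusion-free weeks, not 26. The SAP neither treats that patient as missing nor removes the patient from the denominator, so the patient enters the numerator of TA and stabilized hemoglobin and stays out of the numerator of breakthrough hemolysis. Cutting follow-up short can miss events but cannot create them, so this part of the rule errs only in the drug's favour.

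At stake are proportions and exact intervals that treat time after withdrawal as event-free, in an interim report that may support filings (SAP 4). The plan enrols about 13 to secure 10 evaluable completers, and withdrawals are not replaced (Protocol 14.2 and 8.3.1), so some non-completion is foreseen. One patient weighs most in the naïve and previously eculizumab-treated columns.

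**Working it through.** **Inputs.** The plan states no withdrawal rate, cohort split or expected event rate, so it has no figure of its own to reproduce. SAP 4 limits this SAP to the report after 12 patients are enrolled, so n = 12. The number of event-free other-reason leavers, w, is assumed to be 0 to 3. The upper value borrows the gap between 13 enrolled and 10 completers. Cohort sizes of 4, 5 and 8 are also assumptions.

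**Worst-case bound.** The SAP rule gives x/n, and the bound is (x − w)/n. The exact 95% interval runs from the 2.5% quantile of Beta(x, n − x + 1) to the 97.5% quantile of Beta(x + 1, n − x). When x = n, the lower limit is 0.025^(1/n); for n = 12 this is 0.735. With no events observed in anyone:

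| Column | w | SAP rule (exact lower limit) | Worst-case bound (exact 95% CI) |
|---|---|---|---|
| Total, 12 | 0 | 12/12 (73.5%) | 12/12 (73.5% lower limit) |
| Total, 12 | 1 | 12/12 (73.5%) | 11/12 = 91.7% (61.5 to 99.8) |
| Total, 12 | 2 | 12/12 (73.5%) | 10/12 = 83.3% (51.6 to 97.9) |
| Total, 12 | 3 | 12/12 (73.5%) | 9/12 = 75.0% (42.8 to 94.5) |
| Cohort of 8 | 1 | 8/8 (63.1%) | 7/8 = 87.5% (47.3 to 99.7) |
| Cohort of 5 | 1 | 5/5 (47.8%) | 4/5 = 80.0% (28.4 to 99.5) |
| Cohort of 4 | 1 | 4/4 (39.8%) | 3/4 = 75.0% (19.4 to 99.4) |

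Each such leaver moves the bound by 1/12 = 8.3 points in the total and by 1/5 = 20 points in a cohort of 5. For breakthrough hemolysis the mirror image holds: 0/12 (upper limit 26.5%) becomes 3/12 = 25.0% (5.5 to 57.2) with w = 3.

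**Expected bias.** Let p be the 26-week event risk, with constant hazard −ln(1 − p). Let k patients withdraw for other reasons, at times uniform over 26 weeks and unrelated to the event. A leaver is event-free at withdrawal with probability p/(−ln(1 − p)), but would be event-free at Day 183 with probability 1 − p. Hence

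bias = (k/n) × [p/(−ln(1 − p)) − (1 − p)].

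- p = 0.10: the bracket is 0.9491 − 0.9000 = 0.0491. With n = 12 this is 0.4 points for k = 1 and 1.2 for k = 3.
- p = 0.50: the bracket is 0.7213 − 0.5000 = 0.2213. With n = 12 this is 1.8 points for k = 1 and 5.5 for k = 3.
- Cohort of 5, k = 1: 1.0 to 4.4 points over the same risks.

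**Error of the bound itself.** Counting all k leavers as failures has bias −(k/n)(1 − p). For 3 of 12 this is −0.25 × 0.90 = −22.5 points at p = 0.10 and −0.25 × 0.50 = −12.5 points at p = 0.50. It is a bound and would be a poor replacement estimate.

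**The case against.** The strongest reply is that the information is already planned. Disposition comes with reasons ("along with reason for discontinuation/withdrawal will be presented"), SAP 7.3.1 gives duration of participation, and "By-patient data listings containing all secondary endpoints will be produced". With about 12 patients a reader can count the exact bound. That stands, and it keeps the point small. The disposition table alone does not suffice, because it does not show which leavers already had an event. Suppose 12 patients, 2 completers with an event, and 3 other-reason leavers of whom 1 had an event before leaving. The SAP rule gives 9/12 = 75.0%. Subtracting all three leavers gives 6/12 = 50.0%, whereas the exact bound is 7/12 = 58.3%. The exact figure has to be rebuilt from listings.

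It can also be said that the worst-case row is further from the truth than the rule. On expectation that is so, which is why the row should be a labelled bound beside an unchanged main analysis. SAP 4.2 adopts the lack-of-efficacy half of the rule for consistency with the two adult Phase 3 studies. Keeping the main rule preserves that.

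Four stronger readings are tempting, and the documents do not support them:

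- *The whole withdrawal rule favours the drug.* It does not. Lack-of-efficacy leavers count as failures even if event-free, which errs the other way. Only the other-reason half has a fixed direction.
- *All three are 26-week endpoints by definition.* Breakthrough hemolysis has no stated horizon. Only the handling rule ties it to the Primary Evaluation Period.
- *LOCF is planned here and fails.* Section 7.2.2 does not assign it to these endpoints. The gap is that no sensitivity analysis is specified for them.
- *Nothing is seen after withdrawal.* Protocol 8.3.1 provides an early-termination visit and a call 8 weeks after the last dose covering medications, procedures and adverse events. For a patient last dosed on Day 127 the call falls at about Day 183 (127 + 56). The call brings no central laboratory values, and the SAP rule stops at withdrawal in any case.

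The rule also concerns leaving the study. Patients who only stop drug are encouraged to keep attending visits until they start another complement-targeted therapy (Protocol 8.3.1).

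**Conclusion.** The concern holds as a minor one. The SAP does not say in words that an event-free leaver is a success. That follows from the partial-data rule, the Full Analysis Set definition and the use of a simple proportion, with nothing elsewhere treating such patients as missing. For TA and stabilized hemoglobin it conflicts with the Day 183 definition. For breakthrough hemolysis the same rule applies over the Primary Evaluation Period.

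Confidence in this reading of the text is high, but the size depends entirely on assumed leaver counts, cohort sizes and event risks. With no such leavers the effect is nil. With one to three in 12, the worst-case bound lies 8.3 to 25.0 points below the reported figure, while the expected bias is about 0.4 to 5.5 points. A reader who took the worst-case shifts as the likely error would go beyond the evidence. These are descriptive secondary endpoints with no hypothesis test, and the primary PK/PD endpoint is unaffected.

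**What to change.** Keep the current rule as the main analysis. In SAP 7.2.2 pre-specify, for each of the three endpoints and for the naïve, previously eculizumab-treated and total columns:

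- one added row, with exact 95% interval, that counts every withdrawal before Day 183 as a failure (for breakthrough hemolysis, as an event), labelled as a worst-case bound and not an estimate;
- one footnote giving the number and timing of event-free withdrawals for reasons other than lack of efficacy.

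The cost is SAP wording plus one row and one footnote per endpoint table, with no new data and no change to any headline figure. If nobody leaves this way, the row equals the main result. The downside is that the row overstates failure and may look less favourable than the headline, so the label is essential.
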